5.4.2.5.1. Dermatology Life Quality Index (DLQI)

The DLQI is a dermatology-specific quality of life instrument designed to assess the impact of the disease on a participant's quality of life. It is a 10-item questionnaire that, in addition to evaluating overall quality of life, can be used to assess 6 different aspects that may affect quality of life: symptoms and feelings, daily activities, leisure, work or school performance, personal relationships, and treatment. The DLQI is calculated by summing the score of each question resulting in a maximum of 30 and a minimum of 0. A higher score indicates more severe disease.

A score of ≤ 1 indicates no effect at all of disease on participant's health related quality of life, and a reduction of 5 points or more in total DLQI score is considered clinically meaningful improvement.

For a partially answered questionnaire (eg, not all 10 answers in the DLQI questionnaire were available):

- If one question's answer is not available, this question will be scored 0. The total score will then be calculated.
- If two or more questions' answers are unavailable, the questionnaire is not scored. Hence, the total score and each of the 6 component scores will be set to missing.
- If one question from one of the 6 component scores is missing, the affected component score will be set to be missing.

5.4.2.5.2. Patient-Reported Outcomes Measurement Information System-29 (PROMIS-29)

The PROMIS-29 is a 29-item generic HRQoL survey, assessing each of the 7 PROMIS domains (depression; anxiety; physical function; pain interference; fatigue; sleep disturbance; and ability to participate in social roles and activities) with 4 questions. The questions are ranked on a 5-point Likert Scale. There is also one 11-point rating scale for pain intensity.

The total raw score will be converted into a T-score for each participant based on the table in Appendix 9. The raw score of each domain is converted into a standardized score with a mean of 50 and a standard deviation (SD) of 10 (T-Score). The standardized T-score is reported as the final score for each participant. Pain Intensity is presented as raw responses (0-10). For PROMIS domains of Depression, Anxiety, Physical Function, Pain Interference, Fatigue, a score of 50 is the average for the United States general population with a standard deviation of 10, because testing was performed on a large sample of the general population. However, the other two domains (Ability to Participate in Social Roles and Activities and Sleep Disturbance) were not centered in a national sample. For these two domains, a score of 50 represents the average of the calibration sample which was generally more enriched for chronic illness, and a score of 50 likely represents somewhat sicker people than the general population. A higher PROMIS T-score represents more of the concept being measured. For negatively worded concepts like Anxiety, a T-score of 60 is one SD worse than average. By comparison, an Anxiety T-score of 40 is one SD better than average. However, for positively worded concepts like Physical Function, a T-score of 60 is better than average while a T-score of 40 is better. Participants will undergo this assessment at time points according to the SoA in the protocol.

5.4.2.5.3. Psoriasis Epidemiology Screening Tool (PEST)

The Psoriasis Epidemiology Screening Tool (PEST) is a validated screening tool for psoriatic arthritis. It is a 5-item questionnaire developed to help identify PsA at an early stage. In this study, the PEST will be administered at screening to those who do not report a prior history of confirmed PsA. Those with scores ≥ 3 on screening PEST, may have undiagnosed PsA and will proceed with PsAID-12 at baseline (Week 0) and all subsequent visits. Those who score < 3 on PEST at screening will continue to receive PEST throughout the study.

5.4.2.5.4. PsAID-12

The PsAID-12 is made up of 0-10 numeric rating scale (NRS) questions, with a final result included between 0 (no difficulty)-10 (extreme difficulty). The 12 domains examine different perspectives, both physical and psychological, that are considered important in patients with PsA. Each domain has a different weight: pain, fatigue, and skin problems are those with a greater effect. The PsAID-12 will be administered to all patients with known prior confirmed diagnosis of psoriatic arthritis as well as those who screen positive with score ≥ 3 on PEST at the screening visit.

5.4.2.5.5. Palmoplantar Investigator's Global Assessment (pp-IGA)

The pp-IGA is used to evaluate disease severity of palmoplantar psoriasis. The lesions are assessed in terms of the clinical signs of coloration, thickening, and scaling, which are scored using a 5-point scale: clear (0), almost clear/minimal (1), mild (2), moderate (3), and severe (4).

5.4.2.5.6. Nail Psoriasis Severity Index (NAPSI)

The NAPSI is an index used for assessing and grading the severity of nail psoriasis. Each of the participant's 10 nails is divided into quadrants and is graded for nail matrix psoriasis (pitting, leukonychia, red spots in the lunula, and nail plate crumbling) and nail bed psoriasis (onycholysis, splinter hemorrhages, oil drop discoloration, and nail bed hyperkeratosis). Each quadrant is evaluated for the presence of any of the nail matrix and nail bed features, respectively, with scores ranging from 0 (none of the quadrants) to 4 (all 4 quadrants) impacted. The total individual nail score is the sum of the nail matrix and nail bed score and ranges from 0 to 8. The sum of these scores across all 10 nails represents the total NAPSI score (ranging from 0 to 80 for full hand nails)

NAPSI 50 Responder

Participants with $\geq 50\%$ improvement in NAPSI from baseline will be considered NAPSI 50 responders.

NAPSI 75 Responder

Participants with $\geq 75\%$ improvement in NAPSI from baseline will be considered NAPSI 75 responders.

NAPSI 90 Responder

Participants with $\geq 90\%$ improvement in NAPSI from baseline will be considered NAPSI 90 responders.

NAPSI 100 Responder

Participants with 100% improvement in NAPSI from baseline will be considered NAPSI 100 responders.

5.5. Tertiary/Exploratory Endpoint(s) Analysis

No tertiary/exploratory endpoints in this study.

5.6. Other Safety Analyses

Safety will be assessed by summarizing the occurrences and type of AEs, vital signs (pulse, blood pressure, and weight), examining the changes in the laboratory parameters.

In all the safety analysis, participants who were randomized and received at least 1 (partial or complete) dose of study agent administration will be included and analyzed according to the treatment they actually received, regardless of the treatments they are randomized to.

For all continuous safety variables, descriptive statistics by intervention group will include the N, mean, standard deviation, median, minimum, and maximum. Categorical variables will be summarized by intervention group using frequency counts and percentages.

There are 2 DBLs in this study, respectively, at Week 16, and final DBL at Week 56. Depending on the safety data categories, the cumulative safety data will be analyzed through different study periods which may include, but are not limited to safety data through Week 16, through Week 56. Tabular summaries of safety events for key study periods are in general presented as follows:

Summaries Through Week 16

Safety data through Week 16 will be analyzed according to the following treatment groups:

1. **Placebo:** Participants who received placebo only and no guselkumab through Week 16.
2. **Guselkumab CCI** at Weeks 0, 4, and then **CCI** Participants who received guselkumab **CCI** **CCI** through Week 16.

For participants who started treatment with placebo only but later received guselkumab prior to Week 16 inadvertently, the safety events/measurements on and after the first dose of guselkumab, will be excluded from the data summaries through Week 16. Only the safety events/measurements that occurred while the participants had been receiving placebo only will be included in the data summaries through Week 16.

Summaries Through Week 56

Safety data through Week 56 will be analyzed according to the following treatment groups:

1. **Placebo → Guselkumab CCI CCI** Participants who started treatment with placebo and later received treatment with guselkumab (due to crossed over or inadvertently) at Weeks 16 and 20 then **CCI** through Week 56. All the safety events/measurements that occurred on and after the first dose of guselkumab up to Week 56 will be included in this group.
2. **Guselkumab CCI** Participants who received guselkumab **CCI** at Week 0, 4 and then **CCI** **CCI** through Week 56 for those randomized to guselkumab.

5.6.1. Extent of Exposure

The extent of exposure will be summarized for all treated participants. Descriptive statistics will be presented for number of study agent administrations and cumulative total dose by treatment received.

The exposure data will be summarized for the study periods of:

- Through Week 16
- Through Week 56

Study agent lots received by treatment, including matching placebo for active treatment will also be summarized. In addition, the average exposure (number of administrations) and average duration of follow-up (weeks) will also be summarized by treatment group in the safety tables through different study time periods.

5.6.2. Adverse Events

Adverse Events (AEs) that occurred any time over the study will be reported and coded using Medical Dictionary for Regulatory Activities (MedDRA). Analyses of AEs will be performed on those events that are considered treatment emergent. Treatment emergent AEs are those AEs that occurred after the start of initial study agent administration and those AEs that were present at baseline but worsened in severity after the start of initial study agent administration. Treatment emergent AEs will be summarized by MedDRA system organ class, preferred term, and actual treatment group. The numbers of participants reporting at least 1 event of the following treatment emergent AE categories will be summarized:

- Any AEs
- Serious adverse events (SAEs)
- AEs that are reasonably related to study agent
- AEs of severe intensity
- AEs that led to permanent discontinuation of study agent administration
- Injection-site reactions
- AEs of psoriasis

These summary tables will provide the count and percentage of participants with 1 or more of the specified AEs by treatment group. To adjust for the different duration of follow-up among treatment groups, the AE rates per hundred participant-years of follow-up will also be provided for the above AE categories, Malignancy, Tuberculosis, MACE, infections, serious infections and IBD.

All AE summary tables will include average weeks of follow-up and average number of study agent administrations for each treatment group.

In addition to the summary tables, listings of participants with the following AEs will also be provided:

- SAEs
- AEs leading to permanent discontinuation of study agent
- Opportunistic infection
- Malignancies (non-melanoma skin cancer and other malignancies)
- Death
- Suicidal ideation and behavior
- Possible serum sickness-like reactions and anaphylactic reactions.

Any unfavorable or unintended sign that occurs at the injection site is an injection site reaction and will be recorded as an AE.

Adverse events of psoriasis include any event of erythrodermic psoriasis, pustular psoriasis, guttate psoriasis, inverse psoriasis, palmo-plantar psoriasis and worsening or exacerbation of psoriasis.

In addition, impact of weight on safety will be evaluated for selected treatment emergent AE categories based on baseline weight (≤ 90 kg, >90 kg).

Since safety should be assessed relative to exposure and follow-up, most AE summary tables will include average weeks of follow-up and average number of study agent administrations for each treatment group

5.6.3. Additional Safety Assessments

5.6.3.1. Clinical Laboratory Tests

Blood samples for hematology and clinical chemistry will be collected based on the time and events schedule specified in the protocol. The clinical laboratory parameters to be evaluated by the central laboratory include but are not limited to:

Laboratory Assessments	Parameters		
Hematology	Platelet count	Red Blood Cell (RBC) Indices:	White Blood Cell (WBC) count with
	Red blood cell count	MCV	Differential:
	Hemoglobin	MCH	Neutrophils
			Lymphocytes

Laboratory Assessments	Parameters		
	Hematocrit	% Reticulocytes	Monocytes Eosinophils Basophils
	Note: A WBC evaluation may include any abnormal cells, which will then be reported by the laboratory. A RBC evaluation may include abnormalities in the RBC count, RBC parameters, or RBC morphology, which will then be reported by the laboratory. In addition, any other abnormal cells in a blood smear will also be reported.		
Clinical Chemistry	Sodium Potassium Calcium Chloride Bicarbonate Blood urea nitrogen (BUN) Creatinine Glucose (non-fasting, acceptable) Aspartate aminotransferase (AST) Alanine aminotransferase (ALT) Gamma-glutamyltransferase (GGT)	Total bilirubin Alkaline phosphatase Creatine phosphokinase (CPK) Albumin Total protein	
	Note: Details of liver chemistry stopping criteria and required actions and follow-up are given in protocol Appendix 7: Liver Safety.		
	Potential Hy's Law case (ALT or AST ≥3 x ULN and Tbili ≥2 x ULN) reporting requirements are defined in the protocol section 8.3.1.		
Other	
Lipid Panel (fasting required): Total cholesterol, low-density lipoprotein (LDL), high-density lipoprotein (HDL), triglyceridesSerum Pregnancy Testing for women of childbearing potential onlyHigh-sensitivity C-reactive protein (hsCRP)Serology (HIV antibody, Hepatitis C virus antibody, and Hepatitis B panel which includes: hepatitis B surface antigen [HBsAg], hepatitis B surface antibody [anti-HBs], and hepatitis B core antibody [anti-HBc total])Interferon gamma release assay testing, which includes either QuantiFERON-TB® test or T-SPOT.TB® (for tuberculosis)Follicle-stimulating hormone (screening only to confirm potential post-menopausal status)Hemoglobin A1c (HbA1c)Hepatitis B DNA (screening only for those whose Hepatitis B serology results with HbsAg negative, anti-HBs negative and anti-Hbc total positive)Hepatitis C RNA (screening only for those who are Hepatitis C antibody positive or with history of Hepatitis C treatment)		

Laboratory Assessments	Parameters
	
 Human immunodeficiency virus RNA(screening only; for those whose HIV screen is positive)

The following analyses will be performed as appropriate by actual treatment group:

- Plots of the observed values and changes from baseline over time for selected clinical laboratory parameters
- Number of participants with post-baseline values by maximum toxicity grade according to National Cancer Institute's Common Terminology Criteria for Adverse Events (NCI-CTCAE) for parameters with NCI-CTCAE criteria defined
- Listings of participants with any post-baseline lab value of NCI-CTCAE toxicity Grade 3 or higher

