## Clinical Laboratory Tests

Laboratory data will be summarized by type of laboratory test. Descriptive statistics will be calculated for selected laboratory analytes at baseline and for observed values and changes from baseline at each scheduled timepoint. The number and percentage of participants by maximum National Cancer Institute–Common Terminology Criteria for Adverse Events (NCI-CTCAE) toxicity grades for laboratory analytes with NCI-CTCAE criteria defined will also be summarized, and participants with maximum NCI-CTCAE Grade  $\geq 3$  will also be presented in a listing.

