6.8. Appendix 8 Laboratory Toxicity Grading

The grading scale use for lab assessments is based on 'Common Terminology Criteria for Adverse Events (CTCAE) v5.0'.

If a laboratory value falls within the grading as specified below but also within the local laboratory normal limits, the value is considered to be normal and will be reset to grade 0.

Pre-baseline measurements will use the same grading ranges as applied to baseline measurements. In case a test has two sets of ranges – one for baseline normal and one for baseline abnormal, the one for baseline normal will be applied for all measurements taken pre-baseline and on baseline.

Text in gray italic in the table is present in the grading scale but is not applied by Janssen when grading lab data.

CTCAE Term	Grade 1	Grade 2	Grade 3	Grade 4	Janssen implementation notes
Blood and lymphatic system disorders					
Anemia	Hemoglobin (Hgb) <LLN - 10.0 g/dL; <LLN - 6.2 mmol/L; <LLN - 100 g/L	Hemoglobin (Hgb) <10.0 - 8.0 g/dL; <6.2 - 4.9 mmol/L; <100 - 80g/L	Hemoglobin (Hgb) <8.0 g/dL; <4.9 mmol/L; <80 g/L; transfusion indicated	Life-threatening consequences; urgent intervention indicated	Clinical signs and symptoms are not taken into consideration for grading.
Leukocytosis	-	-	>100,000/mm ³ ; >100 x 10 ⁹ /L	Clinical manifestations of leukocytosis; urgent intervention indicated	Clinical signs and symptoms are not taken into consideration for grading; Added ranges in SI unit (x 10 ⁹ /L)
Investigations					
Activated partial thromboplastin time prolonged	>ULN - 1.5 x ULN	>1.5 - 2.5 x ULN	>2.5 x ULN; bleeding	-	Clinical signs and symptoms are not taken into consideration for grading.
Alanine aminotransferase increased	>ULN - 3.0 x ULN if baseline was normal; 1.5 - 3.0 x baseline if baseline was abnormal	>3.0 - 5.0 x ULN if baseline was normal; >3.0 - 5.0 x baseline if baseline was abnormal	>5.0 - 20.0 x ULN if baseline was normal; >5.0 - 20.0 x baseline if baseline was abnormal	>20.0 x ULN if baseline was normal; >20.0 x baseline if baseline was abnormal	Ranges defined for “abnormal baseline” are applied only if baseline > ULN. If baseline < LLN, then ranges for “normal baseline” are applied.

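### For laboratory tests graded on absolute limits, the maximum post-baseline grade table counts unchanged pre-existing abnormalities as on-treatment toxicity

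*SAP*

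**What the plan says.** SAP 5.6.3.1 plans three laboratory outputs by actual treatment group:

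- line plots, including change since baseline, for a chosen subset of tests
- "Number of participants with post-baseline values by maximum toxicity grade", for parameters that have CTCAE criteria
- "Listings of participants with any post-baseline lab value of NCI-CTCAE toxicity Grade 3 or higher"

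Protocol 9.4.5 plans the same grade summary ("toxicity grades for laboratory analytes with NCI-CTCAE criteria defined will also be summarized"). It also plans baseline and change summaries for some tests: "Descriptive statistics will be calculated for selected laboratory analytes at baseline and for observed values and changes from baseline at each scheduled timepoint".

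For adverse events, SAP 5.6.2 states: "Analyses of AEs will be performed on those events that are considered treatment emergent". An event present at baseline counts there only if it worsened. No matching rule exists for laboratory grades.

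SAP 6.8 (Appendix 8) sets the grades. For ALT, AST, ALP, GGT and bilirubin, a baseline above ULN switches later values to multiples of baseline; for ALT, Grade 1 becomes "1.5 - 3.0 x baseline if baseline was abnormal". The baseline value itself is graded differently: "the one for baseline normal will be applied for all measurements taken pre-baseline and on baseline". Creatinine mixes baseline and ULN ranges. The other routinely collected tests that Appendix 8 grades are judged on absolute or normal-range limits.

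**The concern.** The SAP removes unchanged pre-existing conditions from its adverse event tables but not from its laboratory grade table. For a test graded on absolute limits, someone who enters with an abnormal value and keeps it appears in the same cell as someone who developed the abnormality on treatment.

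Where a concurrent placebo group exists, the reader can at least subtract one column from the other. Where none exists, the participant's own baseline is the only reference, and the grade table does not show it. Carried-over abnormalities could then be read as guselkumab toxicity.

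**Working it through.** The plan states no figure on this point, so there is none to reproduce. The check has four parts.

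**1. Apply Appendix 8 to participants whose value does not change.**

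| Test | Baseline and post-baseline value | Post-baseline grade |
|---|---|---|
| ALT | 1.8 x ULN (ratio to baseline 1.0) | 0 |
| GGT | 4 x ULN (ratio 1.0) | 0 |
| Bilirubin | 1.4 x ULN (ratio 1.0) | 0 |
| Triglycerides | 350 mg/dL (Grade 2 is >300 to 500) | 2 |
| Total cholesterol | 320 mg/dL (Grade 2 is >300 to 400) | 2 |
| CPK | 3 x ULN (Grade 2 is >2.5 to 5 x ULN) | 2 |

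The first three are not counted as toxicity; the last three are. The Grade 3+ listing behaves in the same way: a participant who enters with triglycerides above 500 mg/dL and stays there is listed.

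**2. What entry allows.** Protocol 5.1, criterion 14, applies at screening.

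| Test (low values) | Entry limit | Grade 2 begins below |
|---|---|---|
| Hemoglobin | 10 g/dL | 10 g/dL |
| White cells (x 10^9/L) | 3.5 | 3.0 |
| Neutrophils (x 10^9/L) | 1.5 | 1.5 |
| Platelets (x 10^9/L) | 100 | 75 |

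Low values of these four can be at most Grade 1 at screening, so carry-over affects only their Grade 1 row. Criterion 14 sets no limit on lipids, CPK, electrolytes, albumin, glucose or lymphocytes.

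**3. When a control exists.** In the Schedule of Activities (Protocol 1.3), the lipid panel is drawn at Weeks 0, 24, 48 and 56 and at early termination. Placebo participants cross over at Week 16. Apart from early stoppers, no post-baseline lipid value falls in the placebo-controlled period. Chemistry and hematology are drawn at Weeks 4, 12 and 16, so those tests have a placebo comparison through Week 16. Both Week 56 safety groups in SAP 5.6 are guselkumab groups, so no test has a control there.

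**4. Illustrative dilution through Week 16.** Assumptions, none from the documents: a share b in each arm has an existing grade that persists, and new onset p among the rest is 15% on guselkumab and 5% on placebo. The arm sizes, 200 and 100, are the plan's.

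Tabulated rate = b + (1 - b) x p. Carried-over share = b / tabulated rate.

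At b = 10%: guselkumab 0.10 + 0.90 x 0.15 = 23.5%; placebo 0.10 + 0.90 x 0.05 = 14.5%; carried-over share on guselkumab 10 / 23.5 = 43%.

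| b | Placebo | Guselkumab | Difference (points) | Ratio | Carried over, guselkumab |
|---|---|---|---|---|---|
| 0 | 5.0% | 15.0% | 10.0 | 3.0 | 0% |
| 10% | 14.5% | 23.5% | 9.0 | 1.62 | 43% |
| 20% | 24.0% | 32.0% | 8.0 | 1.33 | 63% |
| 30% | 33.5% | 40.5% | 7.0 | 1.21 | 74% |
| 40% | 43.0% | 49.0% | 6.0 | 1.14 | 82% |

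As a gauge of visibility only, two-proportion normal-approximation power (two-sided 0.05) at b = 10/20/30/40% is 44/29/21/16% on the tabulated rates. On worsened grades alone, with rate (1 - b) x p, it is 70/63/56/48%.

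**The case against.** The strongest reply is that baseline is not ignored and that little depends on this table.

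- A reader might infer that all laboratory grading disregards baseline. It does not. The five liver tests, which bear on a risk named in Protocol 2.3.1, give Grade 0 when an abnormal baseline is unchanged. This stands and limits the point to the other tests.
- A reader might infer that new abnormalities are hidden. They are still counted. Masking occurs only when the same participant already had an equal or higher grade on the same test. This stands.
- Randomization balances carry-over through Week 16, and the table is by grade, so persisting Grade 1 values do not dilute the higher rows. Both are true. Neither helps lipids or the Week 56 summaries.
- Under Protocol 8.2.4, clinically significant abnormal results become adverse events and so fall under the treatment-emergent rule. Changes from baseline are also summarized for selected tests. These are partial safeguards: the first depends on the investigator's judgment, and mean changes do not show who moved between grades.
- No laboratory hypothesis test is planned, so the power figures describe no planned analysis. This stands.
- Replacing the table with a grade-against-baseline-grade comparison for every test would do harm, because the liver tests use two scales. ALT rising from 1.8 to 4.5 x ULN is Grade 1 at baseline and, at 4.5 / 1.8 = 2.5 x baseline, Grade 1 afterwards: not worsened. GGT rising from 4 to 9 x ULN goes from Grade 2 to Grade 1 (9 / 4 = 2.25 x baseline). An unchanged ALT of 1.8 x ULN goes from Grade 1 to Grade 0. Replacement would also drop the summary that Protocol 9.4.5 specifies. This stands and shapes the fix.

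**Conclusion.** The point holds for tests that Appendix 8 grades on absolute limits, and it is minor. For these tests the planned table and the Grade 3+ listing cannot separate a persisting abnormality from one that arose or worsened on treatment. The consequence is clearest for lipids, which have essentially no concurrent control, and for every such test in the Week 56 summaries. Through Week 16 it is dilution that is balanced in expectation.

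That the rule counts unchanged abnormalities follows from the SAP text alone. The size does not: it rests on assumed prevalence, full persistence and assumed onset rates, and the Week 16 illustration does not apply to lipids. The documents do not support reading this as a defect in the planned liver grading or as a threat to the primary analysis.

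**What to change.** In SAP 5.6.3.1, keep the maximum-grade table and add the following for tests without baseline-relative ranges:

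1. A shift table of baseline grade by worst post-baseline grade.
2. A count, by actual treatment group, of participants whose worst post-baseline grade exceeds their baseline grade.

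Show the baseline grade or value in the Grade 3+ listing.

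Leave ALT, AST, ALP, GGT and bilirubin out of the grade comparison unless baseline and post-baseline values are both graded as multiples of ULN. Creatinine likewise needs one common scale before it is included.

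The cost is one additional table and a column in the listing. Appendix 8 already grades baseline values, so no new data are needed.
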